Blood samples for hematology, serum chemistry and serology will be collected. The investigator must review the results, document this review, and record any clinically relevant changes occurring during the study in the AE section of the CRF. Clinically significant abnormal laboratory values should be followed as clinically appropriate or until they return to normal or are otherwise explained by the investigator. Laboratory reports must be filed with the source documents.

The following tests will be performed by the central laboratory:

- **Hematology Panel:**
 - hemoglobin
 - hematocrit
 - red blood cell (RBC) count
 - platelet count
 - white blood cell (WBC) count
 - lymphocytes (%, absolute)*
 - monocytes (%, absolute)*
 - neutrophils (%, absolute)*
 - eosinophils (%, absolute)*
 - basophils (%, absolute)*
- **Serum Chemistry Panel:**
 - sodium
 - potassium
 - chloride
 - blood urea nitrogen (BUN)
 - creatinine
 - glucose
 - aspartate aminotransferase (AST)
 - alanine aminotransferase (ALT)
 - gamma-glutamyltransferase (GGT)
 - total bilirubin
 - magnesium
 - alkaline phosphatase (AP)
 - creatine phosphokinase (CPK)
 - lactic acid dehydrogenase (LDH)
 - uric acid
 - calcium
 - phosphate
 - albumin
 - total protein
 - cholesterol
 - triglycerides
- **Serology:** Samples for HIV antibody, hepatitis B (see [Attachment 3](#)) and hepatitis C virus antibodies will be obtained at screening.
- **Urine Pregnancy Testing** for women of childbearing potential will be done at screening and at the times shown in the TES. Pregnancy tests must be completed and negative at the study visit prior to administration of study drug. All pregnancy test results must be recorded in study source documents.

Vital Signs

Blood pressure and heart rate measurements will be assessed as specified in the TES. If any clinically significant changes in vital signs are noted, they must be reported as AEs and followed to resolution, or until reaching a clinically stable endpoint.

Physical Examination

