- The subject has a reaction resulting in myalgia and/or arthralgia with fever and/or rash (suggestive of serum sickness and not representative of signs and symptoms of other recognized clinical syndromes) occurring 1 to 14 days after an injection of study drug. These may be accompanied by other events including pruritus, facial, hand, or lip edema, dysphagia, urticaria, sore throat, and/or headache.
- Discontinuation of study treatment should be considered for subjects who develop a serious or opportunistic infection. Discussion of such subjects with the medical monitor or designee should also be considered.
- Discontinuation of study treatment for abnormal liver tests is required by the investigator when a subject meets one of the conditions outlined in [Attachment 8A](#) or in the presence of abnormal liver chemistries not meeting protocol-specified stopping rules if the investigator believes that it is in best interest of the subject.

Refer to [Attachment 8B](#) for follow-up assessments (and study treatment restart guidelines) following abnormal liver test results. Study Sponsor must provide written approval before study intervention is restarted.

Subjects who decide to discontinue study drug administration must be interviewed by the investigator to determine if a specific reason for discontinuing study drug can be identified. Subjects should be explicitly asked about the possible contribution of AEs to their decision to discontinue study drug; investigators should confirm that any AE information elicited has been documented. If a subject elects to discontinue study drug due to an AE, the event should be recorded as the reason for study drug discontinuation, even if the investigator's assessment is that the AE would not require study drug discontinuation. The reason for study drug discontinuation must be documented in the eCRF and in source documents. Study drug assigned to a subject who discontinues may not be assigned to another subject.

If a subject discontinues study treatment for any reason before his or her last scheduled injection, he or she should return for the remaining regularly scheduled study visits for at least 12 weeks after receiving the last administration of study drug.

Withdrawal From the Study

A subject will be withdrawn from the study for any of the following reasons:

- Lost to follow-up
- Withdrawal of consent
- Death.

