12.3.2. Serious Adverse Events

All SAEs occurring during the study must be reported to the appropriate Sponsor contact person by study-site personnel within 24 hours of their knowledge of the event.

Information regarding SAEs will be transmitted to the Sponsor using the SAE Form, which must be completed and signed by a physician from the study site, and transmitted to the Sponsor within 24 hours. The initial and follow-up reports of an SAE should be made by facsimile (fax).

All SAEs that have not resolved by the end of the study, or that have not resolved upon discontinuation of the subject's participation in the study, must be followed until any of the following occurs:

- The event resolves
- The event stabilizes
- The event returns to baseline, if a baseline value/status is available
- The event can be attributed to agents other than study drug or to factors unrelated to study conduct
- It becomes unlikely that any additional information can be obtained (subject or health care practitioner refusal to provide additional information, lost to follow-up after demonstration of due diligence with follow-up efforts).

Suspected transmission of an infectious agent by a medicinal product will be reported as an SAE.

Any possible Hy's law case (AST or ALT $\geq 3 \times$ ULN together with bilirubin $\geq 2 \times$ ULN or INR >1.5) is considered an important medical event and must be reported to the sponsor in an expedited manner using the Serious Adverse Event form, even before all other possible causes of liver injury have been excluded. The INR criterion is not applicable to participants receiving anticoagulants.

Any event requiring hospitalization (or prolongation of hospitalization) that occurs during the course of a subject's participation in a study must be reported as an SAE, except hospitalizations for the following:

- Hospitalizations not intended to treat an acute illness or AE (eg, social reasons such as pending placement in long-term care facility)
- Surgery or procedure planned before entry into the study (must be documented in the CRF). Note: Hospitalizations that were planned before the signing of the ICF, and where the underlying condition for which the hospitalization was planned has not worsened, will not be considered SAEs. Any AE that results in a prolongation of the originally planned hospitalization is to be reported as a new SAE.

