Attachment 8: Liver Stopping Criteria and Follow-up Assessments

[figure not shown]
A: Liver chemistry stopping criteria and increased monitoring algorithm

Study intervention will be discontinued for a participant if liver chemistry stopping criteria are met.

Liver Chemistry Stopping Criteria and Increased Monitoring Algorithm

Liver Chemistry Increased Monitoring Algorithm with Continued Study Intervention for Participants with ALT or AST ≥ 3 xULN but < 8 xULN

Abbreviations: ALT = alanine transaminase; AST = aspartate transaminase, INR = international normalized ratio; SAE = serious adverse event; ULN = upper limit of normal, Tbili = Total bilirubin.

Refer to [Attachment 8B: Liver Safety: Suggested Actions and Follow-up Assessments and Study Intervention Rechallenge Guidelines](#).

B: Liver chemistry stopping criteria and follow-up assessments

Study intervention will be discontinued for a participant if liver chemistry stopping criteria are met.

Liver Chemistry Stopping Criteria and Follow-Up assessments

Liver Chemistry Stopping Criteria	
ALT or AST-absolute	ALT or AST $\geq 8 \times \text{ULN}$
ALT or AST-Increase	ALT or AST $\geq 5 \times \text{ULN}$ but $< 8 \times \text{ULN}$ persists for ≥ 2 weeks ALT or AST $\geq 3 \times \text{ULN}$ but $< 5 \times \text{ULN}$ persists for ≥ 4 weeks
Bilirubin^{1, 2}	ALT or AST $\geq 3 \times \text{ULN}$ and total bilirubin $\geq 2 \times \text{ULN}$ ($> 35\%$ direct bilirubin)
INR²	ALT or AST $\geq 3 \times \text{ULN}$ and international normalized ratio (INR) > 1.5
Cannot Monitor	ALT or AST $\geq 5 \times \text{ULN}$ but $< 8 \times \text{ULN}$ and cannot be monitored weekly for ≥ 2 weeks ALT or AST $\geq 3 \times \text{ULN}$ but $< 5 \times \text{ULN}$ and cannot be monitored weekly for ≥ 4 weeks
Symptomatic³	ALT or AST $\geq 3 \times \text{ULN}$ associated with symptoms (new or worsening) believed to be related to liver injury or hypersensitivity
Suggested Actions, Monitoring, and Follow up Assessments	
Actions	

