4. PK sample may not be required for participants known to be receiving placebo or non-comparator interventions. Record the date/time of the PK blood sample draw and the date/time of the last dose of study intervention prior to the PK blood sample draw on the CRF. If the date or time of the last dose is unclear, provide the participant's best approximation. If the date/time of the last dose cannot be approximated OR a PK sample cannot be collected in the time period indicated above, do not obtain a PK sample. Instructions for sample handling and shipping are included in the pertinent Study Reference Manual.

Liver Chemistry Increased Monitoring Criteria with Continued Study Intervention

Liver Chemistry Increased Monitoring Criteria and Actions with Continued Study Intervention	
Criteria	Actions

ALT or AST $\geq 5 \times \text{ULN}$ and $< 8 \times \text{ULN}$ and total bilirubin $< 2 \times \text{ULN}$ or INR < 1.5 without symptoms believed to be related to liver injury or hypersensitivity, and who can be monitored weekly for 2 weeks
 
OR
 
ALT or AST $\geq 3 \times \text{ULN}$ and $< 5 \times \text{ULN}$ and total bilirubin $< 2 \times \text{ULN}$ or INR < 1.5 without symptoms believed to be related to liver injury or hypersensitivity, and who can be monitored weekly for 4 weeks
	
 • Notify the sponsor within 24 hours of learning of the abnormality to discuss participant safety • Participant must return weekly for repeat liver chemistry tests (ALT, AST, alkaline phosphatase, total bilirubin) until the abnormalities resolve, stabilize, or return to baseline • If at any time the participant meets liver chemistry stopping criteria proceed as described in the pertinent manual • If ALT or AST decreases from ALT or AST $\geq 5 \times \text{ULN}$ and $< 8 \times \text{ULN}$ to $\geq 3 \times \text{ULN}$ but $< 5 \times \text{ULN}$, continue to monitor liver chemistries weekly • If, after 4 weeks of monitoring, ALT or AST $< 3 \times \text{ULN}$ and total bilirubin $< 2 \times \text{ULN}$, monitor participants twice monthly until liver chemistry tests resolve, stabilize, or return to baseline

References:

EASL Clinical Practice Guidelines: Drug-induced liver injury. *Journal of Hepatology* 2019; 70 (6):1222-1261.

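### In the written Attachment 8B tables, a subject with bilirubin below 2×ULN can stay on drug under weekly liver monitoring without INR ever being drawn, so the INR stopping row can go unchecked

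*Protocol*

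**What the plan says.** Protocol Attachment 8B contains two tables that bear on the same subjects.

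- **Stopping table.** ALT or AST ≥3×ULN stops drug if total bilirubin is ≥2×ULN with more than 35% direct, or if INR is above 1.5. Footnote 1 also stops drug when bilirubin is ≥2×ULN and fractionation is not immediately available. Footnote 2 exempts subjects on anticoagulants from the INR threshold. The attachment opens with the rule "Study intervention will be discontinued for a participant if liver chemistry stopping criteria are met".
- **Continue-dosing table (increased monitoring).** Both of its ALT/AST bands, 3 to below 5×ULN and 5 to below 8×ULN, admit a subject with bilirubin below 2×ULN "or INR < 1.5 without symptoms believed to be related to liver injury or hypersensitivity", provided weekly attendance is possible. The weekly action is: "Participant must return weekly for repeat liver chemistry tests (ALT, AST, alkaline phosphatase, total bilirubin) until the abnormalities resolve, stabilize, or return to baseline". A further line says: "If at any time the participant meets liver chemistry stopping criteria proceed as described in the pertinent manual".

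Three other places matter. Section 9.6 lists the hematology and chemistry panels under "The following tests will be performed by the central laboratory", and neither includes INR. Section 12.3.2 says that ALT or AST ≥3×ULN with bilirubin ≥2×ULN or INR above 1.5 "is considered an important medical event and must be reported to the sponsor in an expedited manner using the Serious Adverse Event form", and adds that "The INR criterion is not applicable to participants receiving anticoagulants". Section 10.2 points to Attachment 8A for the mandatory stopping conditions and to 8B for follow-up. It also allows discontinuation for "abnormal liver chemistries not meeting protocol-specified stopping rules if the investigator believes that it is in best interest of the subject".

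**The concern.** INR is one of the two laboratory markers that turn a raised transaminase into a stopping event and a possible Hy's law report. The continue-dosing table manages the subjects who are closest to that event and still on drug. If its entry test can be passed without an INR, and its weekly panel never asks for one, the INR stopping row exists on paper but nothing in the schedule feeds it. The instruction to act if a stopping criterion is met at any time does not help, because it cannot act on a value that nobody has measured.

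The connector is a second, lesser problem. The stopping table stops on either abnormal marker. The continue table asks for only one acceptable marker, so a subject with one abnormal marker can meet both.

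At stake is individual patient safety and complete expedited reporting. The week-68 comparison is not involved.

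**Working it through.** The plan gives no figure to reproduce here. The check codes the two tables as rules and compares them.

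**Rules, for ALT/AST 3 to below 8×ULN, no symptoms, able to attend weekly, persistence rows not yet reached**

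- Stop (S): bilirubin ≥2×ULN with more than 35% direct or not fractionated; or INR >1.5 without anticoagulant.
- Continue (C), as written: bilirubin <2×ULN **or** INR <1.5.

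**As written**

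| Bilirubin | INR <1.5 | INR =1.5 | INR >1.5, no anticoagulant | INR >1.5, on anticoagulant |
|---|---|---|---|---|
| <2×ULN | C | C | S and C | C |
| ≥2×ULN, >35% direct | S and C | S | S | S |
| ≥2×ULN, not fractionated | S and C | S | S | S |
| ≥2×ULN, ≤35% direct | C | neither | S | neither |

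Stop = 1 + 4 + 4 + 1 = 10. Continue = 4 + 1 + 1 + 1 = 7. Both = 3. Neither = 2. Check: 10 + 7 − 3 + 2 = 16.

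**What happens if INR is not measured.** In the first row, bilirubin <2×ULN makes the continue condition true whatever the INR. The cell with INR >1.5 and no anticoagulant, which should stop, then looks the same as its neighbours. Where INR is specified:

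| Setting | INR specified? |
|---|---|
| Routine panels, Section 9.6 | No |
| Weekly panel, continue-dosing table | No |
| Repeat panel after stopping, higher-risk branch | Yes |
| Repeat panel after stopping, lower-risk branch (bilirubin <2×ULN **and** INR ≤1.5) | Yes |

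The attachment therefore requires INR for lower-risk subjects already off drug, but not for comparable subjects kept on drug.

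In the fourth row, entry to the continue table needs INR <1.5, so INR is known at entry. It is not repeated in the weekly panel, so a later rise is not looked for.

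**With bilirubin <2×ULN and INR ≤1.5 (INR not applied on anticoagulants)**

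| Bilirubin | INR <1.5 | INR =1.5 | INR >1.5, no anticoagulant | INR >1.5, on anticoagulant |
|---|---|---|---|---|
| <2×ULN | C | C | S | C |
| ≥2×ULN, >35% direct | S | S | S | S |
| ≥2×ULN, not fractionated | S | S | S | S |
| ≥2×ULN, ≤35% direct | neither | neither | S | neither |

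Stop = 10, continue = 3, both = 0, neither = 3. Check: 10 + 3 + 3 = 16. If *and* were combined with a strict INR <1.5, INR of exactly 1.5 with bilirubin <2×ULN would meet neither table, so ≤ is needed.

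The edit raises the neither count from 2 to 3. Bilirubin ≥2×ULN with ≤35% direct and INR <1.5 now receives weekly tests and 24-hour sponsor notification through the continue table, and would lose both unless the fix keeps them.

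**The case against.** **The Attachment 8A algorithm may govern.** Section 10.2 takes the mandatory stopping conditions from 8A, and one of its algorithms is titled for exactly this ALT/AST range. The figures are not in the supplied text. The abbreviation list beneath them defines INR, so 8A evidently uses it, but how cannot be seen. This stands as a limit on the claim. A correct 8A would still leave 8B's explicit weekly list without INR.

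**Stopping takes priority.** The attachment's opening rule and the continue table's own line both send a subject who meets a stopping criterion out of continued dosing. A reader might infer from the *or* that the protocol tells sites to keep dosing despite an abnormal marker. It does not: in the three overlapping cells the text as a whole says stop. What remains of the connector is untidy wording, plus its role in letting a subject in without an INR.

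**A direct-fraction gap.** A reader might also infer that bilirubin ≥2×ULN with ≤35% direct and INR <1.5 is a possible Hy's law case being kept on drug, because Section 12.3.2 has no direct-fraction condition. Footnote 2 of 8B does have one (more than 35% direct), and under it the pattern is not possible Hy's law. The two places differ on what to report, and a reporting duty does not by itself conflict with continued dosing. Their INR arms agree, so the point made here does not depend on that difference.

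**Practical exposure is small.** Sites must notify the sponsor within 24 hours, may take unscheduled samples, and must follow clinically significant abnormal values as appropriate. Re-treatment chemistry is drawn at R0, R16 and R28, and no study dose follows R16. All of this is fair and keeps the point minor. None of it requires an INR.

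**Conclusion.** The point holds for the written 8B tables. A subject with ALT/AST 3 to below 8×ULN and bilirubin below 2×ULN can be kept on drug with INR never drawn. The INR stopping row and the INR arm of the possible Hy's law report then cannot be triggered from any specified panel. An INR that rises after entry is also not looked for. The bilirubin stopping row is not affected, because bilirubin is in the weekly panel.

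The size is minor. The documents give no event rate. The overall safety SAP, Section 4.5, counts 236 subjects who started re-treatment. That is an upper bound for re-treatment under this text, because the liver attachment came with Amendment 5 in June 2021. The documents do not say how many other subjects were dosed under it. Re-treatment doses are 8 weeks apart, persistence rows force a stop after 2 or 4 weeks, and the overall safety SAP describes the final re-treatment analysis as performed.

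A reader might go further and infer that no dose can ever fall inside the monitoring period. The documents do not support that. Weekly monitoring continues when ALT/AST falls from the upper to the lower band, so the two persistence periods could run in sequence and approach 2 + 4 = 6 weeks. An unscheduled draw can also come shortly before a dose. A missed report, moreover, does not depend on a further dose. The primary endpoint and sample size are unaffected.

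**What to change.** In Attachment 8B:

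1. In both bands of the continue-dosing table, require bilirubin <2×ULN *and INR ≤ 1.5 (INR criterion not applied to subjects on anticoagulants)*.
2. Add INR to the weekly panel.
3. In the line on meeting a stopping criterion, refer to the 8B stopping table instead of an unnamed manual.
4. Add a line that any subject with ALT/AST ≥3×ULN who meets neither table, including bilirubin ≥2×ULN with ≤35% direct, keeps weekly testing and 24-hour sponsor notification. Dosing is then decided by the investigator under Section 10.2 with sponsor review.

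Check the 8A figures against the edited text, and correct any template that carries the same wording. Because sponsor notification was already required, the sponsor should be able to identify subjects managed under this table and see whether an INR was obtained.

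The cost is a few wording edits in one attachment and one INR test on weekly draws that already take place. The remaining drawback is that the three patterns with bilirubin ≥2×ULN and ≤35% direct that meet no stopping row rest on judgement, but under continued weekly testing.

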
 • Immediately discontinue study intervention • Report the event to the sponsor within 24 hours • Complete the liver event reporting form and complete an SAE CRF if the event also met the criteria for an SAE² • Perform follow-up assessments as described in the Follow up Assessment column • Monitor the participant until liver chemistry test abnormalities resolve, stabilize, or return to baseline 
MONITORING:
 
If ALT or AST $\geq 3 \times \text{ULN}$ AND total bilirubin $\geq 2 \times \text{ULN}$ or INR > 1.5:
 
 • Repeat liver chemistry tests (include ALT, aspartate transaminase [AST], alkaline phosphatase, total bilirubin and INR) and perform liver event follow-up assessments within 24 hours • Monitor participant twice weekly until liver chemistry test abnormalities resolve, stabilize, or return to baseline • A specialist or hepatology consultation is recommended 
If ALT or AST $\geq 3 \times \text{ULN}$ AND total bilirubin $< 2 \times \text{ULN}$ and INR ≤ 1.5:
 
 • Repeat liver chemistry tests (include ALT, AST, alkaline phosphatase, total bilirubin and INR) and perform liver chemistry follow-up assessments within 24 to 72 hours • Monitor participants weekly until liver chemistry abnormalities resolve, stabilize, or return to baseline 
RESTART/RECHALLENGE
	
 • Viral hepatitis serology⁴ • Obtain blood sample for PK-analysis as quick as possible after the most recent dose⁴ • Obtain serum creatine phosphokinase (CPK), lactate dehydrogenase (LDH), gamma-glutamyltransferase [GGT], and glutamate dehydrogenase [GLDH], and serum albumin • Fractionate bilirubin if total bilirubin $\geq 2 \times \text{ULN}$ • Obtain complete blood count with differential to assess eosinophilia • Record the appearance or worsening of clinical symptoms of liver injury, or hypersensitivity, on the liver event reporting form • Record use of concomitant medications (including acetaminophen, herbal remedies, recreational drugs, and other over-the-counter medications) • Record alcohol use on the liver event alcohol intake form 
If ALT or AST $\geq 3 \times \text{ULN}$ AND total bilirubin $\geq 2 \times \text{ULN}$ or INR > 1.5 obtain the following in addition to the assessments listed above:
 
 • Anti-nuclear antibody, anti-smooth muscle antibody, Type 1 anti-liver kidney microsomal antibodies, and quantitative total immunoglobulin G (IgG) or gamma globulins • Serum acetaminophen adduct assay, when available, to assess potential acetaminophen contribution to liver injury in participants with definite or likely acetaminophen use in the preceding week

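### Attachment 8B lets one enzyme below 3×ULN trigger the step-down to twice-monthly liver tests, so on a literal reading one narrow course falls under both the weekly and the twice-monthly action

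*Protocol*

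**What the plan says.** The text in question is the Actions column of the last table in Attachment 8B, which covers closer liver monitoring while study drug continues. A subject enters with ALT or AST at 5–<8×ULN or at 3–<5×ULN, without liver symptoms. The actions that matter here are:

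- Sponsor contact: "Notify the sponsor within 24 hours of learning of the abnormality to discuss participant safety".
- General rule: "Participant must return weekly for repeat liver chemistry tests", until the abnormality has resolved, stabilised or returned to baseline.
- Stopping rows take precedence: "If at any time the participant meets liver chemistry stopping criteria proceed as described in the pertinent manual".
- Partial fall, from 5–<8×ULN into 3–<5×ULN: "continue to monitor liver chemistries weekly".
- Step-down: "If, after 4 weeks of monitoring, ALT or AST" is below 3×ULN and total bilirubin is below 2×ULN, then "monitor participants twice monthly until liver chemistry tests resolve, stabilize, or return to baseline".

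The stopping table earlier in 8B ends treatment at once at 8×ULN or more. It also ends treatment when 5–<8×ULN persists for at least 2 weeks, or 3–<5×ULN for at least 4 weeks. Nothing in the text of 8B says that both enzymes must be below 3×ULN before step-down. Nothing ranks the step-down action against the partial-fall action.

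**The concern.** In the entry and stopping rows the wording *ALT or AST at or above a limit* is right: either enzyme is enough to raise concern. The opposite of that condition is that both enzymes are below the limit. The step-down action reverses the inequality but keeps the *or*. If only ALT was ever raised, AST meets the enzyme condition from the first day, and that part of the rule tests nothing.

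The same attachment handles such a reversal correctly elsewhere. In the monitoring instructions for subjects taken off drug, the high-risk branch joins bilirubin and INR with *or*, and the low-risk branch joins them with *and*.

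This is a rule for subjects who remain on drug. A site that followed it to the letter could miss the weekly test at which the 4-week stopping row would be seen to be met.

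**Working it through.** No figure in the plan has to be reproduced. The check is one of logic and timing.

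**Inputs.** From Attachment 8B: the bands, the 2-week and 4-week persistence rows, and the two competing actions. Assumed: ALT 6×ULN falling to 4×ULN, AST 2×ULN throughout, bilirubin below 2×ULN, INR not above 1.5, no symptoms, weekly tests at weeks 0 to 4. The bilirubin assumption fits a subject still on drug, because 8B has a stopping row for raised bilirubin together with an enzyme at 3×ULN or more.

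**Which actions apply at ALT 4, AST 2?**

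- Partial fall: earlier ALT 6 lies in 5–<8 and current ALT 4 lies in 3–<5, so **true**.
- Step-down as worded: (4 < 3 or 2 < 3) and bilirubin below 2 = (false or true) and true = **true**.
- Step-down requiring both enzymes: (4 < 3 and 2 < 3) and bilirubin below 2 = (false and true) and true = **false**.

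**Can a subject reach week 4 in this state?** The table shows every ALT course that never rises, starts at 6 or 4×ULN and is still at 3×ULN or more at week 4. Persistence is counted within each band.

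| ALT (×ULN), weeks 0–4 | Stopping row | At week 4 |
|---|---|---|
| 6, 4, 4, 4, 4 | none; 4 − 1 = 3 weeks in 3–<5 | both actions apply |
| 6, 6, 4, 4, 4 | none; 4 − 2 = 2 weeks in 3–<5 | both actions apply |
| 6, 6, 6, 4, 4 | 5–<8 for 2 weeks, at week 2 | already stopped |
| 6, 6, 6, 6, 4 | same, at week 2 | already stopped |
| 6, 6, 6, 6, 6 | same, at week 2 | already stopped |
| 4, 4, 4, 4, 4 | 3–<5 for 4 weeks, at week 4 | stopping governs |

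Two courses remain: the fall first seen at week 1, and the fall first seen at week 2. Courses that drop below 3×ULN and rise again were not enumerated.

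**Delay if the literal step-down is taken at week 4.** Assume twice monthly means every 14 to 15 days. The next test is then at 4 + 14/7 = week 6.00 or 4 + 15/7 = week 6.14.

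- Fall seen at week 1: stop due at 1 + 4 = week 5. Delay (6.00 − 5) × 7 = 7 days, or (6.14 − 5) × 7 ≈ 8 days. The skipped week-5 test is the one that would have shown it.
- Fall seen at week 2: stop due at 2 + 4 = week 6. Delay 0 days, or (6.14 − 6) × 7 ≈ 1 day.

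**Sensitivity.** If persistence runs from the first value at or above 3×ULN, both courses reach 4 weeks at week 4. The stopping action then governs and there is no overlap.

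**Dosing.** Section 6 of the protocol gives Part 2 and re-treatment injections 8 weeks apart. If the rise is found at such a visit, the next injection is at week 8, after all these dates.

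**The case against.** The strongest reply is that no sensible site would act this way. The partial-fall action can only refer to the enzyme that was raised, and the step-down action uses the same phrase directly after it. The ordinary reading is therefore that the raised enzyme has come below 3×ULN. The general weekly rule, the specific partial-fall rule and the overriding stopping rule all point to the right action, and the sponsor is already involved within 24 hours. The overlap also needs the persistence clock to restart when ALT changes band. A subject who went from 6× to 4×ULN would then stay on drug longer than one steady at 4×ULN, which is hardly intended. Finally, the Attachment 8A algorithm for this same pathway is a figure that cannot be seen in the text, and it may settle the matter.

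All of this stands as a limit on size. It does not make the operator right: 8B still states a condition that differs from the one evidently meant.

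A reader might also infer that 8B contradicts itself in two other places. After drug is stopped, similar values call for "Monitor participants weekly until liver chemistry abnormalities resolve, stabilize, or return to baseline". The Cannot Monitor row ends treatment for a subject at 3–<5×ULN "and cannot be monitored weekly for" 4 weeks or more. Neither is a direct conflict. The first covers subjects already off drug, and the second covers subjects who cannot attend weekly, whereas the subject here has attended. They show only how closely the authors meant to watch values in this range.

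**Conclusion.** The point holds as a minor wording error in an on-drug safety rule. With bilirubin below 2×ULN, one enzyme below 3×ULN satisfies the step-down as written. A subject with no stopping row met, ALT down from 5–<8 to 3–<5×ULN and AST below 3×ULN then falls under both the weekly and the twice-monthly action.

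Among the courses examined, the overlap at week 4 arises only when the fall is first seen at week 1 or 2 and persistence is counted by band. The worst outcome is one skipped weekly test and a stop recognised about 7 to 8 days late, given a 14-to-15-day interval. The documents do not say how many subjects, if any, would follow such a course.

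A reader might conclude that subjects on drug would in practice be monitored too little, or that the trial's results are exposed. The documents support neither. The surrounding actions make a wrong step unlikely, and the rule does not enter the design, the endpoints or any analysis. Nor can one say that the protocol as a whole leaves the step-down unclear while the 8A figure is unseen.

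**What to change.** In the step-down action of Attachment 8B, require both ALT and AST below 3×ULN and total bilirubin below 2×ULN. Leave the thresholds and test intervals as they are. With that wording the example meets only the weekly action, and the overlap disappears. At the same time, check that the Attachment 8A figure says the same.

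The cost is a one-phrase clarification. It adds no tests beyond the weekly ones that the other actions already require.
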